10.4.3. Study Phases for Concomitant Medication

No study phases will be defined for concomitant medications; all concomitant medications taken will be summarized together.

10.5. Appendix 5: Data Display Standards & Handling Conventions

10.5.1. Reporting Process

Software	

 The currently supported versions of SAS software will be used. 	
Reporting Area	
HARP Server	: uk1salx00175
HARP Compound	: GSK1325756
Analysis Datasets	

 Analysis datasets will be created according to CDISC standards (SDTM IG Version 3.2 & ADaM IG Version 1.1). 	
Generation of RTF Files	

 RTF files will be generated for all tables in the final reporting effort. 	

10.5.2. Reporting Standards

General	

 The current GSK Integrated Data Standards Library (IDSL) will be applied for reporting, unless otherwise stated (IDSL Standards Location: https://spope.gsk.com/sites/IDSLLibrary/SitePages/Home.aspx): 
 4.03 to 4.24: General Principles 5.01 to 5.08: Principles Related to Data Listings 6.01 to 6.11: Principles Related to Summary Tables 7.01 to 7.13: Principles Related to Graphics 	
Formats	
	
 GSK IDSL Statistical Principle 4.24 for decimal places (DP's) will be adopted for reporting of data based on the raw data collected, unless otherwise stated. Numeric data will be reported at the precision collected on the eCRF. The reported precision from non eCRF sources will follow the IDSL statistical principles but may be adjusted to a clinically interpretable number of DP's. Summaries of continuous data will include number of participants, mean, standard deviation (SD), median, minimum and maximum. Percentages between 1% and 99%, inclusive, will be rounded to integers. Percentages greater than 0%, but less than 1%, will be reported as <1%, and percentages greater than 99%, but less than 100%, will be reported as >99%. Actual time will be reported as HH:MM. Seconds will not be presented.
Planned and Actual Time	
	
 Reporting for tables, figures and formal statistical analyses: 
 Planned time relative to dosing will be used in figures, summaries and statistical analyses. Calculation of derived PK parameters will use actual time. The impact of any major deviation from the planned assessment times and/or scheduled visit days on the analyses and interpretation of the results will be assessed as appropriate. Reporting for Data Listings: 
 Planned and actual time relative to study drug dosing will be shown in listings (Refer to IDSL Statistical Principle 5.05.1).

 Unscheduled or unplanned readings will be presented within the participant's listings. 	
Unscheduled Visits	

 Unscheduled visits will not be included in summary tables or figures. All unscheduled visits will be included in listings. 	
Descriptive Summary Statistics	
Continuous Data	Refer to IDSL Statistical Principle 6.06.1
Categorical Data	N, n, frequency, %
Graphical Displays	

 Refer to IDSL Statistical Principles 7.01 to 7.13. 	

10.5.3. Reporting Standards for Pharmacokinetics

Pharmacokinetic Concentration Data	
PC Windows Non-Linear (WNL) File	PC WNL file (CSV format) for the non compartmental analysis by Clinical Pharmacology Modelling and Simulation function will be created according to Standards for the Transfer and Reporting of PK Data document. Note: Concentration values will be imputed as per GUI_51487
Descriptive Summary Statistics, Graphical Displays and Listings	Refer to IDSL PK Display Standards. Refer to IDSL Statistical Principle 6.06.1. Note: Concentration values will be imputed as per GUI_51487 for descriptive summary statistics/analysis and summarized graphical displays only.
Pharmacokinetic Parameter Derivation	
PK Parameter to be Derived by Programmer	None
Pharmacokinetic Parameter Data	
Is Not Quantifiable (NQ) impacted PK Parameters Rule Being Followed	No (PK parameter derivation is not expected to be affected by NQs.)
Descriptive Summary Statistics (Log Transformed parameters AUCs, Cmax, t1/2)	Refer to IDSL PK Display Standards. N, n, geometric mean, 95% CI of geometric mean, SD of logged data and [between or within] geometric coefficient of variation (CV _{b/w} (%)) will be reported. $[1] \text{ CV}_b \text{ (%)} = \sqrt{(\exp(\text{SD}^2) - 1) * 100}$ $(\text{SD} = \text{SD of log transformed data})$ $[2] \text{ CV}_w \text{ (%)} = \sqrt{(\exp(\text{MSE}) - 1) * 100}$ $(\text{MSE} = \text{mean square error from mixed effect model of log-transformed data}).$
Untransformed Parameters	Tmax, tlag, and tlast
PK Parameters listed only	lambda_z, lambda_z_lower, lambda_x_upper, No_points_lambda_z

10.6. Appendix 6: Derived and Transformed Data

10.6.1. General

Multiple Measurements at One Analysis Time Point

 ○ The mean of the triplicate vital sign assessments as recorded on the eCRF will be reported; all individual assessments will be listed. ○ The mean of the triplicate ECG assessments will be calculated and reported; all individual assessments will be listed. The baseline ECG assessment will be calculated as described in Section 5.2 Baseline Definitions. ○ For any other parameter with multiple measurements at one time point, the mean of the measurements will be calculated and used in any derivation of summary statistics but if listed, all data will be presented.
Study Day

 ○ Calculated as the number of days from first study treatment dose date: 
 ● Ref date = missing → study day = missing ● Ref date < first study treatment dose date → study day = ref date – first study treatment dose date ● Ref date ≥ first study treatment dose date → study day = ref ate – (first study treatment dose date) + 1
Period Study Day

 ○ Period day refers to the study day within a period. 
 ○ For period 1, period day will be the same as study day. ○ For period 2, period day will be calculated as (ref date – 2nd treatment dose date + 1). ○ For period 3, period day will be calculated as (ref date – 3rd treatment dose date + 1). ○ For period 4, period day will be calculated as (ref date – 4th treatment dose date + 1).
Study Completion Definition

 ○ A participant is considered to have completed the study if they have not withdrawn and were dosed in their last scheduled treatment period.

10.6.2. Study Population

Demographic Characteristics
Age

 ○ GSK standard IDSL algorithms will be used for calculating age where birth date will be imputed as follows: 
 ○ Any participant with a missing day will have this imputed as day '15'. ○ Any participant with a missing date and month will have this imputed as '30th June'. ○ Birth date will be presented in listings as 'YYYY'. ○ Age will be calculated based on the Screening visit date.
Body Mass Index (BMI)

 ○ Calculated as Weight (kg) / [Height (m)²]

Compliance	
Compliance with OMP	

 ○ An OMP dose scheduled to be taken in the clinic will be counted if the answer to 'Did the subject receive the correct treatment' in the OMP dosing section of the eCRF is 'Yes'. ○ The total number of OMP doses taken will be calculated as the sum of each dose taken in the clinic on Days -4, -1, 1, 2, and 3 and the actual number of doses taken at home between Day -4 and Day -1 (as recorded in the eCRF). ○ Compliance with OMP will be calculated as: Total doses taken*100/(number of days between Day -4 and Day 3) ○ Compliance with OMP will be summarized as a continuous variable and also in the categories: 
 ○ <80% ○ 80-<120% ○ ≥120% 	

Meals	

 ○ The duration of the meal (in minutes) will be calculated and summarized as a continuous variable. ○ The proportion of the meal consumed will be summarized as a continuous variable and also in the categories: 
 ○ <90% ○ 90-<95% ○ ≥95% ○ The actual time between the start of the meal and the time of dosing will be summarized as a continuous variable and also in the categories: 
 ○ <20 min ○ 20-<40min ○ ≥40 min 	

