**Part B**

In Part B, approximately 24 healthy elderly participants will be enrolled such that approximately 20 subjects (10 subjects per group) complete dosing and critical assessments for all planned treatment periods in Group 1 and 2.

In Part B Group 2 eligible participants will take omeprazole (OMP), 40 mg from Day -4 relative to treatment period 1, Day 1 first dose of danirixin through all periods and washouts until the final treatment period 3 PK assessment (48hr post dose). Participants will be provided with a participant diary to document daily recordings of OMP dosing occurring outside of the unit.

For Part B Group 2, once screened, eligible participants will be instructed to return to the clinic on Day -4 relative to the first dose of danirixin on Day 1 (Period 1) for a qualification visit. During this visit, clinical safety assessments will be performed as specified in the Section 2 Schedule of Activities of the protocol. Once assessments are complete, eligible participants will be administered a single dose of OMP in the clinic. Participants will be discharged with OMP and will take OMP on Day -3 and Day -2 at home. OMP will be administered in the clinic on Day -1, Day 1, Day 2 and Day 3 of each treatment period. OMP will be taken on an outpatient daily bases on all other days through each period until the Period 3 post dose 48h PK assessment.

For Group 1 and 2, eligible participants will be admitted to the clinical facilities on Day -1 of each treatment period.

On Day 1 of each treatment period, following completion of the required pre-dose measurements and procedures, the investigator or authorized study unit personnel will administer a single oral dose of 50 mg danirixin to each participant in the unit. Following dosing, participants will undergo clinical safety assessments and serial PK assessments at timepoints specified in the Section 2. Participants will be discharged from the unit approximately 24 hours following dosing at the Investigator's discretion.

Participants will return back to the unit on an outpatient basis approximately 48 hours post dose for the 48 hour post dose assessments and be discharged once the assessments are complete at the investigator's discretion. Three to ten days following the last dose of danirixin, participants will return to the clinic for the final follow-up visit. Refer to Section 2 for study assessments and timepoints.

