7.2.4. Strategy for Intercurrent Events

Participants who experienced the following intercurrent events will have data from the relevant treatment period excluded from analysis:

- Received incorrect formulation or meal
- Did not consume at least 90% of the meal (in fed participants)
- Missed more than one OMP dose between Days -4 and -2 or missed any other OMP dose (participants on treatments I, J, K – Section 5.1 Study Treatment Display Descriptors))
- Did not provide an adequate PK concentration profile to allow reliable estimation of PK parameters

Inclusion of the participant's remaining data in the analysis effectively uses a missing at random assumption to account for the excluded data.

If a participant is included in the PK population but withdrew from the study prior to a treatment period, data for that and subsequent periods will not be imputed. Inclusion of

the participant's data prior to withdrawal in the analysis effectively uses a missing at random assumption to account for the missing data.

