10. APPENDICES

10.1. Appendix 1: Protocol Deviation Management

PDs will be tracked by the study team throughout the conduct of the study in accordance with the Protocol Deviation Management Plan (PDMP) for the study:

- PICTS database is not being used to collect protocol deviations occurring in the study. A PD spreadsheet (PD Log) is being used to collect all deviations from the protocol and is being managed by the IQVIA Clinical Research Associate.
- Every time there is a deviation, an email is sent to the GSK study team to confirm whether it should be classified as important or not, and subsequently updated in the spreadsheet.
- Participants who received an incorrect formulation or meal, consumed <90% of meal or were non-compliance with OMP will be captured as an important protocol deviation.
- The spreadsheet will be reviewed prior to SDL to ensure all important deviations are captured.
- At the end of the study, IQVIA will convert this spreadsheet into a SAS dataset which will be provided to statistics and programming along with the other datasets.
- This dataset will be the basis for the summaries and listings of PDs.
- Important PDs (including deviations related to study inclusion/exclusion criteria, conduct of the trial, participant management or participant assessment) will be summarised and listed.
- A separate summary and listing of all inclusion/exclusion criteria deviations will also be provided. This summary will be based on data as recorded on the inclusion/exclusion page of the electronic case report form (eCRF).
- A Per Protocol Population will not be defined.

The following PDs will lead to exclusion from the pharmacokinetic parameter analysis outputs for the specific period (tables, statistical analysis and figures). Exclusions will be programmed by statistics and programming from the SDTM data:

- incorrect meal/formulation
- non-compliance with OMP (participants on treatments I, J, K – Section 5.1 Study Treatment Display Descriptors))
- consumed <90% of meal (in fed participants)

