Admission to Unit			X														
Laboratory Assessments	X		X														X

Procedure	Screening (Up to 30 days prior to Day 1) ¹	Qualification Visit Day -4 ⁹	Day -1	Study Day (Treatment Periods -1-3) ²												Early Discontinuation /Follow-up (3 to 10 days post-last dose)	
				Pre-dose	0h	0.5h	1h	1.5h	2h	3h	4h	6h	8h	10h	12h	24h	
(include liver chemistries)																	
12-lead ECG ⁴	X		X						X								X
Vital Signs ⁵	X			X												X	X
Randomization				X													
Meal ⁶				X													
Danirixin Administration ⁷					X												
Omeprazole Administration ⁸		X	X		X											X	X
Diary Card completion for Omeprazole Dosing				←-----→													
Pharmacokinetic Sampling				X	X	X	X	X	X	X	X	X	X	X	X	X	

Procedure	Screening (Up to 30 days prior to Day 1) ¹	Qualification Visit Day -4 ⁹	Day -1	Study Day (Treatment Periods -1-3) ²												Early Discontinuation /Follow-up (3 to 10 days post-last dose)	
				Pre-dose	0h	0.5h	1h	1.5h	2h	3h	4h	6h	8h	10h	12h	24h	
SAE Review				←-----→													
AE Review			X		←-----→												
Concomitant Medication Review			X		←-----→												
Discharge																X	

1. Screening must be performed within 30 days prior to receiving the dose of Danirixin on Day 1 of period 1.
2. Treatment periods 1-3 will include a minimum 5 day wash-out from day of dose between each treatment.
3. Serum pregnancy test (where applicable) will be performed at the screening visit and a urine pregnancy test at all other time points specified.
4. Triplicate ECGs at screening and on Day -1 of each treatment period only. Single ECGs at other timepoints (performed at a similar time of day as Day 1 Pre-dose), unless a reading meets the QTc stopping criteria, in which case two further measurements will be taken at the same time point and the average values captured.
5. Triplicate BP and HR assessments at screening and pre-dose on Day 1 of each treatment period only. Single measurements at other timepoints (performed at a similar time of day as Day 1 Pre-dose). HR and BP assessments only performed at the 24 and 48 hr post dose and early discontinuation/follow-up visit timepoints.
6. Meal (where applicable) to be started and completed within 30 minutes prior to danirixin dosing. Normal and high fat meal will be described in the SRM.

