7. When danirixin dosing occurs in the fasted state, participants will be provided with a light snack and then will fast from all food and drink (except water) from 10 hours prior to dose until 4 hr post-dose on Day 1 in each treatment period at which time lunch will be provided. An evening meal will be provided at approximately 9 h post dose. At all other times during residency in the clinic, meals will be provided at appropriate times.
8. OMP will be taken starting on Day -4 continuing daily through all treatment and washout periods until the day of the Period 3, 48hour PK assessment. The Day -4 Qualification visit only applies to period 1.

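### The omeprazole compliance formula fits only Period 1: at the minimum 5-day dose interval, a fully compliant participant scores 71% or 86% in Periods 2 and 3

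*SAP*

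**What the plan says.** **The formula (SAP 10.6.2, Compliance with OMP).** The numerator is "each dose taken in the clinic on Days -4, -1, 1, 2, and 3 and the actual number of doses taken at home". Home doses are limited to those from Day -4 to Day -1, and their count is taken from the eCRF. The denominator is the number of days from Day -4 to Day 3. The percentage is shown as a continuous variable and in three categories: below 80%, 80% to below 120%, and 120% or more.

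**Where it is applied.** SAP 6.1 and Table 1.15 summarise it by treatment for I, J and K. Under the sequences in SAP 2.3, each Group 2 participant takes I, J and K in three different periods. A by-treatment summary therefore needs one score per period.

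**The dosing schedule.** Protocol Synopsis, Part B: "OMP will be administered in the clinic on Day -1, Day 1, Day 2 and Day 3 of each treatment period". OMP is taken at home on the remaining days, including Days -3 and -2 before Period 1. SAP 10.2.1, Part B Group 2 footnotes: "The Day -4 Qualification visit only applies to period 1", and "Treatment periods 1-3 will include a minimum 5 day wash-out from day of dose between each treatment".

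**The PK exclusion.** SAP 7.2.4 drops a period under I, J or K if the participant "Missed more than one OMP dose between Days -4 and -2 or missed any other OMP dose". SAP Appendix 1 shortens this to non-compliance with OMP and adds: "Exclusions will be programmed by statistics and programming from the SDTM data".

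**The concern.** One formula serves three periods, but its terms are those of Period 1. The Day -4 clinic dose belongs to a visit that does not recur. The home-dose term assumes that the days just before Day -1 are spent at home. With short intervals, some of them are still clinic days of the previous period.

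The compliance table is what a reader uses to judge whether acid suppression was in place for the OMP comparisons (I vs E, J vs F, K vs G) and for the food comparisons under OMP. A table showing poor compliance where there was none would cast doubt on those results for no reason.

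There is a second, conditional worry. SAP 7.2.4 uses a Day -4 to Day -2 window for all three OMP treatments without saying how it is resolved in Periods 2 and 3. If the exclusion flag were built from the same period-labelled fields as the percentage, doses that were taken could be read as missed.

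**Working it through.** The plan states no compliance figure, so the benchmark is the formula applied to Period 1. Clinic Days -4, -1, 1, 2 and 3 give 5, and home Days -3 and -2 give 2. The days from Day -4 to Day 3, with no Day 0, number 7. Full compliance is (5 + 2)/7 = 100%, so 7 is the denominator that makes the formula work. A denominator of 6 would give 7/6 = 116.7%, and 8 would give 7/8 = 87.5%.

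**Mapping Periods 2 and 3.** Put the previous danirixin dose at time 0 and the next at time d days. The previous period's clinic Days 1, 2 and 3 fall at times 0, 1 and 2. Day -k of the new period falls at time d - k.

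- d = 5: Day -4 is time 1 (previous Day 2, clinic), Day -3 is time 2 (previous Day 3, clinic), Day -2 is time 3 (home).
- d = 6: Day -4 is time 2 (previous Day 3, clinic), Days -3 and -2 are home.
- d of 7 or more: Days -4, -3 and -2 are all home.

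The current period always supplies 4 clinic doses (Days -1, 1, 2, 3). For a participant who takes every dose:

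| Dose interval d | Period-labelled records | Day -4 dose credited by date |
|---|---|---|
| 5 days | (4 + 1)/7 = 71.4% | (5 + 1)/7 = 85.7% |
| 6 days | (4 + 2)/7 = 85.7% | (5 + 2)/7 = 100% |
| 7 days or more | (4 + 3)/7 = 100% | 100% |

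At 5 days, crediting by date does not restore 100%. The Day -3 dose was taken in the clinic, but Day -3 is not a listed clinic day, and the dose is not a home dose either. The last row assumes that a home dose on Day -4 itself counts; if not, it is 6/7 = 85.7%.

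**Effect on the table if every interval were 5 days.** Twelve participants in six equal sequences is 2 per sequence. Each treatment comes first in two sequences, so 4 participants take it in Period 1 and 8 in Periods 2 or 3. With perfect compliance throughout, each treatment column would show 8 of 12 below 80%, with a mean of (4 × 100 + 8 × 71.4)/12 = 81%. With the Day -4 dose credited by date, none would be below 80% and the mean would be (4 × 100 + 8 × 85.7)/12 = 90%.

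**Exclusion window.** By calendar date, this participant has 0 missed doses in Days -4 to -2 at any interval and is kept. From period-labelled fields there would be 2 apparent misses at 5 days (more than one, so excluded), 1 at 6 days (kept) and 0 at 7 or more (kept).

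**Day numbering.** SAP 10.6.1 sets period day in Periods 2 and 3 to the date minus that period's dose date, plus 1. The day before dosing is then Day 0. In Period 1, which uses study day, it is Day -1. Under the period-day formula, Day -4 to Day 3 spans eight dates in Periods 2 and 3 (-4, -3, -2, -1, 0, 1, 2, 3) against seven in Period 1.

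**The case against.** The strongest objection concerns the exclusion. A reader might infer that the plan would discard Periods 2 and 3 for all of Group 2, which is 2 × 12 = 24 of 3 × 12 = 36 planned periods. The documents do not support this. SAP 7.2.4 excludes on doses actually missed; it neither uses the percentage nor refers to 10.6.2. The 24 of 36 needs every interval to be exactly 5 days and the flag to be programmed from period-labelled fields. There are also checks. SAP Appendix 1 records OMP non-compliance as an important deviation, has each deviation confirmed with the sponsor's study team, and has the log reviewed before Source Data Lock. Table 1.9 and Listing 7 show the PK exclusions, and Listing 11 shows OMP dosing times. Mass exclusion with no matching deviations would be conspicuous. This part of the objection stands.

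It can also be said that Day -4 is defined relative to Period 1 (Protocol Synopsis, Part B), so the window in 7.2.4 may be leniency for the lead-in only, with every later dose falling under the second clause. That reading is possible, and the SAP does not settle it. It does not rescue 10.6.2: if Day -4 exists only in Period 1, the formula has no defined window for the other two periods that the by-treatment table must report.

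Third, 5 days is a minimum. SAP 10.4.1 places washout on the days strictly between two doses, so five full washout days would mean a 6-day interval and a score of at least 86%, in the middle category. This limits the 71% but does not remove it, because the schedule footnote counts the 5 days from the day of dose.

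Finally, the percentage feeds one descriptive table and no model. That is correct and bounds the consequence.

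**Conclusion.** The concern holds for the compliance formula. As written, it under-reports full compliance in Periods 2 and 3 at the permitted minimum interval: 71% from period-labelled records, 86% if the Day -4 dose is credited by date. The gap narrows at 6 days and closes at 7 or more, provided a home dose on Day -4 counts. The main consequence is a misleading Table 1.15.

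For the PK analysis there is only a risk to close. Losing compliant periods is not a consequence of the text of 7.2.4; it would take a programming choice that the SAP leaves open.

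The figures rest on a 7-day denominator and on intervals at or near the minimum; the documents do not give the intervals actually used. The 71% also assumes that each clinic dose is stored under the period in which it was given. The eCRF layout is not in the documents.

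**What to change.** - **SAP 10.6.2.** For every period, take the four calendar days before the danirixin dose and Days 1 to 3. Score each day one if an OMP dose is recorded on that date, wherever it was taken and under whichever period it is stored. Divide by 7. Full compliance is then 7/7 = 100% in every period.
- **SAP 7.2.4 and Appendix 1.** Derive the exclusion flag from date-level OMP dose records, not from the total out of 7, because the effect of one missed dose depends on its day. State whether the Day -4 to Day -2 window recurs in Periods 2 and 3 and which doses fall under the second clause. At a 5-day interval, Day 3 of one period is also Day -3 of the next, so a single real miss there comes under a different clause for each period.
- **SAP 10.6.1.** Use one day numbering for all periods, so that Day -4 means the same thing in each.

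The cost is SAP wording and a small programming change. No new data should be needed: clinic dose dates and times are recorded, and home doses are kept in a daily diary. The sponsor should confirm that home doses are held by date, because 10.6.2 refers to them as a number recorded in the eCRF. If only a count is held, the dates would have to be taken from the diaries.
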